16. SAFETY OUTCOMES

The Safety Analysis Set (SAS) will be used for all safety analyses. All adverse event tables will be summarized by treatment group. There will be no statistical comparisons between the treatment groups for safety data, unless otherwise specified.

16.1. Adverse Events

16.1.1. Treatment Emergent Adverse Events

Treatment-emergent adverse events (TEAEs) are defined as AEs that begin or worsen after the first dose of double-blind IMP and through the end of the study including the Follow-up Period. For an AE that has a start date on the same day as first dose (DFDOSE) or has a (partially or completely) missing start date, it is considered as treatment-emergent if the answer to the CRF question “Did this event start prior to first dose of study medication post-randomization (double-blind)” is No.

Note that for positively adjudicated tendon rupture events, treatment-emergent is defined based on the adjudicated tendon rupture diagnosis date being on or later than the date of first dose (DFDOSE).

Severity (Protocol Section 13.1.4) is classed by the investigator as mild, moderate, or severe (increasing severity). TEAEs with missing severity will be grouped as severe in summary tables. If a patient reports a TEAE more than once within that SOC/PT, the AE with the worst-case severity will be used in the corresponding severity summaries.

[figure not shown]
Relationship to study IMP is assessed by the Investigator. For tabulation, a TEAE is considered as related, with a relationship of “possibly related”, “probably related”, or “definitely related” to study IMP, or if the relationship is missing.

The patient incidence of AEs will be summarized for all treatment-emergent AEs (TEAEs), serious TEAEs (SAEs), by preferred term in descending order of frequency in the active treatment group.

Patient incidence of all treatment-emergent AEs (TEAEs), serious TEAEs, treatment-related TEAEs and AEs leading to withdrawal of IMP will be tabulated by SOC and PT in descending order of frequency.

In addition, an overall summary of adverse events, incidence of serious TEAE and TEAE leading with withdrawal of IMP by SOC and PT will be provided for patients in the SAS with baseline use of ezetimibe.

16.1.2. Adverse Events of Special Interest

 AESIs will be identified by specified MedDRA PTs, or the related laboratory criteria if applicable. See [Appendix 7](#) for the list of AESIs and their definitions. These events will be summarized by AESI category, laboratory criteria met (if applicable), and PTs.

The NODM AESI is applicable only for patients with baseline glycemic status ([Section 7.4](#)) of No Diabetes at baseline. As an AESI vs. an efficacy endpoint, NODM includes a broader definition of NODM with patients who meet one of the following conditions:

- patients with verified NODM as determined by the DC ([Section 7.4.3](#)), or
- patients who initiated a diabetes medication after first dose of IMP ([Appendix 8](#)), or
- patients meeting the laboratory criteria for NODM as in [Appendix 7](#), or
- patients with selected AE preferred terms (see list of preferred terms for ‘NODM’ in [Appendix 7](#)).

Worsening Hyperglycemia AESI is applicable to patients with baseline glycemic status of Diabetes based on adverse event preferred terms as described in [Appendix 7](#).

See [Appendix 7](#) for the list of AESIs and their definitions. AESIs will be identified by specified MedDRA PTs, and/or the related laboratory criteria if applicable. These events will be summarized by treatment group, and by AESI category, laboratory criteria met, and PTs.

Malignancy AESI will be summarized by Standardised MedDRA Queries (SMQs) and PTs as described in [Appendix 7](#).

Tendon rupture will be summarized for events that are positively adjudicated according to the TRAC Charter. All potential tendon ruptures that were reviewed by the TRAC will be presented in a listing.

For AEs considered to be muscle related by the Investigator, additional information is collected on the *Muscle Related Adverse Event Complementary* CRF including the primary cause, locations, and whether the AE is unilateral or bilateral.

16.1.3. Other Adverse Events

TEAEs of *Gout* and *Gouty Arthritis* will be summarized by patients’ medical history of gout and by their baseline uric acid category according to the central laboratory normal range (low/normal, versus high).

16.1.4. Exposure Adjusted Incidence Rates (EAIRs) of TEAEs

For all treatment-emergent AEs, SAEs, and AESIs, exposure-adjusted incidence rates (EAIR) will be calculated by preferred terms (PTs) and by treatment group.

For the calculation of EAIR, the duration of exposure for each patient is from the date of the first dose of IMP to the date of the first event (PT), or the DLASMT ([Section 7.2.1](#)) if the patient did not experience the event in question. For each event, the EAIR is calculated as the number of events (the first event, so each patient is counted only once) divided by the sum of duration of exposure over all patients in the SAS in the treatment group. It will be expressed as per 100 patient-years.

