10.6. Procedures and Schedule of Assessments

The study is comprised of 3 distinct periods: screening, run-in, and double-blind treatment.

The schedule of study events is provided in Appendix 1. However, a patient can be seen at any time for reasons of safety.

Note: If the patient discontinues IMP at any time after T1, please proceed to Section 10.7 for detailed instructions.

- If the patient agrees to clinical visits after withdrawing from IMP at any time after Visit T1, the visit will include all procedures and assessments except for those pertaining to IMP management (IMP dispensing, adherence, and accountability).
- If the patient agrees to telephone or other form of contact after withdrawing from IMP at any time after Visit T1, the contact will include collection of patient-reported information to complete the eCRF including concomitant medication use, AEs, SAEs, and potential clinical endpoints.
- Patient is expected to continue to receive IMP and complete study visits following a clinical endpoint unless, for some reason, this is no longer clinically appropriate.

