10.7.3. Permanent Discontinuation of Investigational Medicinal Product

There may be situations where it may be necessary for a patient to permanently discontinue IMP.

Investigators should contact the Medical Monitor prior to permanent IMP discontinuation to discuss the situation. **If IMP is permanently discontinued, the patient will remain in the study to be evaluated for concomitant medications, efficacy and safety endpoints until the final study visit.** If the patient is unwilling or unable to return for follow-up visits in person, alternatives such as telephone contact visits per the Schedule of Events, or telephone follow up bi-annually, annually or at the end of the study will be offered. The follow-up frequency will be documented in the eCRF.

The reason for permanent discontinuation of IMP should be documented in the eCRF. If the discontinuation of IMP is due to an AE, the event should be documented in the eCRF. Some possible reasons that must lead to permanent early IMP discontinuation include:

- Female patients who become pregnant or are breastfeeding or who do not agree to use an acceptable method(s) of birth control during the study will be permanently discontinued from IMP
- The patient requests to stop IMP permanently
- The patient study blind is broken
- Patient moves away and it is impossible to come to this or any other trial site for visits as required by protocol.

Some possible reasons that may lead to permanent early IMP discontinuation include:

- In the opinion of the investigator, any AE or a significant change in a laboratory value that warrants permanent discontinuation of IMP therapy. Investigators are advised to call the Medical Monitor prior to making such a decision.
- Illness, condition, or procedural complication (including AEs) affecting the patient's ability to participate or requiring prohibited medication. Investigators are advised to call the Medical Monitor prior to making such a decision.
- Enrollment in any other clinical trial involving an investigational product or enrollment in any other type of medical research judged not to be scientifically or medically compatible with this study. If, after discussion with the study Medical Monitor, it is determined that the patient should not continue IMP, IMP will be discontinued.

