7.2. Key Study Dates

7.2.1. Definition and Imputation of Key Event Dates

Date of End of Study (EOS): the study completion/early termination date recorded on the “Study Completion/Early Termination” CRF. Note that the patient may have a 30-day post EOS follow-up visit after this.

Date of Study Completion (DSC): For patients who did not complete the study, it is the later of a) the date of EOS and b) the date of the 30-day post EOS follow-up visit. For patients who completed the study, it is the latest date of a) the date of EOS, b) the date of the 30-day post EOS follow-up visit, or c) the date of death. This date is used to calculate the duration of study (follow-up) for each patient and all clinical events that happen during this period are adjudicated.

Date of First Dose of IMP (DFDOSE): for each patient, the DFDOSE is the date/time of administration recorded on the “On-Site Study Medication/ Compliance” CRF at Visit T1. If that field is missing, it is set to be next first date of administration at Visit T3.

Date of Last Dose of IMP (DLDOSE): the date of last dose is recorded on the End of Treatment CRF. In cases of missing either completely or partially, it is imputed as the earliest date of a) the last day of the month (if the month and year are present), or the last day of the year (if only the year is present); b) the Date of EOS; and c) the date of the last IMP dispense plus the number of tablets taken.

Date of Last Visit (DLVISIT): the last date recorded on either the *Visit Date* or the *Telephone Contact* CRFs. For patients who did not complete the study, this must be on or prior to the DSC.

Date of Last Known Alive (DALIVE): for patients whose vital status at the end of study is either alive or unknown, this is the last day when the patient is known to be alive. It is the latest “last known alive date” recorded on the *Survival Status* CRF. If this date is partially or completely missing, it is set to the later of last known alive date with imputation and DSC.

Date of Last Assessment for Non-Fatal Clinical Endpoints (DLASMT): Potential clinical endpoints are assessed every three months either in clinic or by telephone through the Post-EOS Phone visit. For patients who died during the study within 90 days of last visit, the DLASMT is set to the date of death. Otherwise, the DLASMT is set to be DLVISIT. Note that this definition also applies to new-onset diabetes mellitus (NODM) as an efficacy endpoint.

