14. STUDY MEDICATION COMPLIANCE AND EXPOSURE

The time from randomization to IMP discontinuation (last dose) will be summarized by treatment groups, and presented using a Kaplan-Meier plot for all patients in the FAS. Patients not dosed will have a time of 0.

In addition, estimated compliance with study IMP will be presented for the FAS by treatment groups. The patients will be grouped as compliant, i.e., those who have $\geq 80\%$ of required tablets (taken once daily) while on treatment, versus noncompliant ($<80\%$ compliance).

The percentage compliance calculation will be based on the tablet counts using the formula:

$$\text{Total \# of tablets taken} = \sum_{\text{bottles}} (100 - (\# \text{ of tablets returned}))$$

as each bottle of double-blind IMP contains 100 tablets. If a dispensed bottle is not returned, it is assumed that the patient has taken all the tablets and the number of tablets returned is set to be zero (0).

$$\% \text{compliance} = \frac{[\text{total \# of tablets taken}]}{[\# \text{ of days between last and first doses}]}$$

The percentage compliance is capped as a maximum of 100% if it exceeds 100% due to the imputation above.

Note that patients who did not receive any IMP will be counted as noncompliant (0%). In addition, if a patient did not return any bottles, he/she will also be counted as noncompliant (0%).

Exposure to the study treatment is based on the duration (in years) between the last and first doses, and will be presented for the SAS by treatment groups. Exposure will also be presented for patients in the SAS with baseline ezetimibe use.

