15.2.4. Sensitivity Analyses of Primary Efficacy Endpoint

In the primary analysis, censoring is assumed to be uninformative, i.e., patients who were censored share a common hazard function as those who were not censored in the same treatment group. However, there is a key difference between them as the censored patients also by definition stopped the treatment, while the majority of those remained on-study were still on-treatment. To evaluate the potential impact, two sensitivity analyses will be performed:

- Multiple imputation analysis: the hazard function for patients after censoring is assumed to be the same as those patients who were assigned the same treatment, had stopped treatment but remained in the study follow-up longer. The data from those patients with follow-up will be used as the model for imputation of the time to events for the censored patients.
- Tipping point (TP) analyses: The goal of this analysis is to explore the plausibility of unobserved data assumptions under which the conclusions change. Unlike the standard multiple imputation analysis, the censored patients in the active treatment group are allowed to have the same or even worse outcome than those in the placebo group. A range of assumed hazard ratios (vs placebo) will be used to evaluate when the estimated treatment effect starts to “tip”, i.e., becoming in favor of the placebo.

The details of the analyses are specified in Appendix 6.

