15.4.2. On-Treatment Analysis

An on-treatment analysis will also be conducted for primary time to 4-component MACE (MACE-4) and 3-component MACE (MACE-3) endpoints in the PPS.

The sensitivity analyses will also be performed for the time to first occurrence of NODM on treatment for patients with baseline glycemic status of no diabetes, prediabetes, or normoglycemic in the PPS.

For these on-treatment analysis, events (MACE-4, MACE-3 or NODM) that occurred after DLDOSE + 30 days will be ignored. Patients who did not have events before that will be censored at the earlier of the DLDOSE + 30 days and DLASMT, the date of censoring for non-fatal events defined in Section 7.2.5.

[figure not shown]
On-treatment analyses will be performed for lipid parameters and biomarkers including LDL-C, HDL-C, non-HDL-C, total cholesterol, triglyceride, hs-CRP, HbA_{1C} and fasting glucose. For these endpoints, values measured more than 7 days after the Date of Last Dose of IMP will be excluded, and only observed values prior to that will be summarized by treatment groups, and for HbA_{1C} and fasting glucose also by baseline glycemic status.

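### Is the adverse-event rate in SAP 16.1.4 wrongly called exposure-adjusted because its person-time runs on after study drug is stopped?

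*SAP*

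**What the plan says.** SAP 16.1.4 divides the number of patients with a first event of a given preferred term by summed person-time over the Safety Analysis Set, per 100 patient-years. The duration "for each patient is from the date of the first dose of IMP to the date of the first event (PT), or the DLASMT". SAP 7.2.1 sets DLASMT to the date of death if the patient died within 90 days of the last visit. "Otherwise, the DLASMT is set to be DLVISIT", which is the last clinic or telephone contact.

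SAP 16.1.1 counts as treatment-emergent those "AEs that begin or worsen after the first dose of double-blind IMP and through the end of the study including the Follow-up Period".

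Stopping the drug does not end safety follow-up. Under Protocol 10.7.3, "the patient will remain in the study to be evaluated for concomitant medications, efficacy and safety endpoints until the final study visit". Protocol 10.6 has patients who agree only to telephone or other contact give the information needed "to complete the eCRF including concomitant medication use, AEs, SAEs, and potential clinical endpoints".

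SAP 14 describes a different quantity: "Exposure to the study treatment is based on the duration (in years) between the last and first doses".

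The last-dose cuts in SAP 15.4.2 belong to the efficacy sensitivity analyses. There, "events (MACE-4, MACE-3 or NODM) that occurred after DLDOSE + 30 days will be ignored", and lipid and biomarker values have a 7-day cut.

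**The concern.** A reader who meets the word exposure in both SAP 14 and SAP 16.1.4 may take the adverse-event rate to be a rate while on drug. It is not: a patient who stops at Month 6 and is followed to Month 42 contributes 36 months of time off drug. If a drug-related excess fades after stopping, that time dilutes the difference between arms.

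The SAP also seems to treat the matter unevenly. For MACE it notes that "the censored patients also by definition stopped the treatment, while the majority of those remained on-study were still on-treatment" and plans on-treatment analyses. For adverse events the available text plans no last-dose cut, and the subgroup rates in SAP 16.1.5 use the same definition. At stake would be the reading of serious events and events of special interest: a signal that looks smaller than it is, or a rate that cannot be reconciled with the exposure table.

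**Working it through.** The plan states no figure for this rate, so there is none to reproduce. The check has three parts.

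**1. Do numerator and denominator match?**

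| Element | Starts | Ends | Source |
|---|---|---|---|
| Events counted | first double-blind dose | end of study, including follow-up | SAP 16.1.1 |
| Person-time | first dose | first event, else last contact or death within 90 days of it | SAP 16.1.4, 7.2.1 |
| Event collection after stopping drug | – | continues | Protocol 10.6, 10.7.3 |

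They match. A faulty rate would count events over one window and time over another. Protocol 13.1.7 also defines treatment-emergent events with no cut at last dose, so the SAP follows the protocol.

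**2. Is the wording inconsistent within the SAP?** Section 15.5.4 computes MACE incidence rates and also calls time from randomization to first event or censoring the duration of exposure. Both rate sections thus use that phrase for time at risk. Section 14 speaks of exposure to the study treatment and means dosing time. Each term is defined where it is used.

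Counts divided by Section 14 time will not give the 16.1.4 rate, but this is true of any time-to-first-event rate. A patient on drug for 3.5 years with the event at 1 year adds 3.5 years to Section 14 and 1 year to the rate. A rate cut at last dose plus 30 days would not match Section 14 either.

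**3. How far apart are the two rates?** Assumptions:
- Follow-up *T* is uniform over 24 to 57 months. This is the 24-month minimum plus about 33 months of enrolment (SAP 8.1), so the mean is 3.375 years.
- Permanent stopping is exponential at *s* = 4, 8 or 12% per year. The documents give no rate.
- The excess ends *w* = 30 days after last dose, and background risk is the same on and off drug.

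Mean time from first to last dose is E[(1 − e^(−sT))/s]. The share of person-time more than 30 days after last dose is f = E[(T − w) − (1 − e^(−s(T−w)))/s] / E[T]. For rare events the follow-up ratio is about 1 + (RR − 1)(1 − f).

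| *s* per year | First to last dose (years) | 3.375 ÷ that | f | RR 2.0 reads | RR 1.5 reads |
|---|---|---|---|---|---|
| 4% | 3.146 | 1.07 | 6.5% | 1.94 | 1.47 |
| 8% | 2.939 | 1.15 | 12.4% | 1.88 | 1.44 |
| 12% | 2.750 | 1.23 | 17.7% | 1.82 | 1.41 |

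For *s* = 8%: 1 + 1 × (1 − 0.124) = 1.88.

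Other assumptions change the picture (background 1 per 100 patient-years):
- *Excess persists after stopping:* 2.0 reads 2.0.
- *Off-drug background doubled, stopping 12% v 8%, true ratio 1.1:* the follow-up difference is 0.135 per 100 patient-years against 0.100 on treatment, so it moves away from the null.
- *Informative stopping:* half the patients have 1.6 and half 0.4 times the average hazard. Active-arm stopping averages 12% and is 1.7 and 0.3 times that in the two halves; placebo stopping is 8%, unrelated to risk. With no drug effect, the planned rate gives a ratio of 1.00 and a rate cut at last dose plus 30 days gives 0.92. At a true 1.5 both give 1.38.

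**The case for a change.** The strongest case is that the SAP sees that being on or off drug matters for MACE and plans last-dose cuts there, yet plans no companion rate for serious events and events of special interest. A reader who takes the label literally will misread the table, and one supplementary table from dates already derived would prevent this.

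Part of this stands. A label such as patient-years of follow-up would be plainer, and an on-treatment rate would answer a further legitimate question.

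The rest does not. SAP 15.2.4 asks whether censoring of MACE-4 is uninformative, and SAP 15.4.2 describes efficacy sensitivity analyses, with the MACE and diabetes ones in the Per-Protocol Set. Neither implies that safety tables need the same cut. Relabelling changes no result. The added rate would not be a truer one: it drops events that appear after stopping, which matters for delayed harms such as malignancy, and it can look protective when high-risk patients stop earlier. The plan already gives context through events leading to withdrawal of study drug (SAP 16.1.1) and time to discontinuation by arm (SAP 14). SAP 15.4.4, 17, 18 and Appendix 7 are not in the available text and Protocol 13.3 is redacted, so it cannot be said that no on-treatment summary exists.

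**Conclusion.** The concern does not hold. SAP 16.1.4 defines a coherent follow-up rate: events and time share one stated window, the protocol's definition supports it, and the SAP uses the term the same way in Section 15.5.4. Followed as written, it gives sound descriptive safety results. SAP 16 plans no between-arm testing of safety data unless otherwise specified, so no test rests on these rates.

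The gap from an on-drug rate is modest under the assumptions shown: 2.0 reads 1.94 to 1.82 for stopping of 4 to 12% per year. It vanishes if the excess persists and can reverse if patients who stop carry higher background risk. Its size and direction rest on stopping rates and off-drug risks that the documents do not give. It measures the distance between two estimands, not an error in either. Whether to add an on-treatment table is a matter of preference.

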7.4. Diabetes Related Definitions

7.4.1. Baseline Glycemic Status

Analyses of diabetes and related biomarkers are conducted with specific subsets of study population based on the baseline glycemic status defined in Table 1.

- For efficacy analyses of new-onset type 2 diabetes (conducted in the study population with No Diabetes at baseline), and related biomarkers HbA1c and fasting glucose, the FAS (or PPS for sensitivity analyses) is used with subpopulations defined according to the baseline glycemic status.
- For safety analyses of AESIs of *new-onset diabetes* (conducted in the study population with No Diabetes at baseline), and *worsening hyperglycemia* (Diabetes at baseline), and related safety laboratory measures including HbA1c and fasting glucose, the SAS is used with subpopulations defined according to the baseline glycemic status.

Table 1: Baseline Glycemic Status

Status	Definition
Diabetes	Meeting 1 or more of the following criteria at baseline captured by information recorded prior to Day 1: 
 • Medical history or adverse events indicating diabetes as defined in the Diabetes Committee Charter (attached as Appendix 8) • Prior glucose-lowering medication as defined by the Diabetes Committee Charter (attached as Appendix 8) • HbA_{1C} measurement $\geq 6.5\%$ • Two or more measurements of fasting glucose ≥ 126 mg/dL (7.0 mmol/L)
Inadequately Controlled (IC) Diabetes	With Diabetes and a HbA _{1C} of 7% or greater at baseline.
No Diabetes	Not meeting any of the criteria for Diabetes at baseline.
Prediabetes	No Diabetes at baseline, and with: 
 • HbA_{1C} measurement of $\geq 5.7\%$ and $< 6.5\%$, OR • 1 or more measurements of fasting glucose ≥ 100 mg/dL (5.6 mmol/L), but not more than 1 value of fasting glucose ≥ 126 mg/dL (7.0 mmol/L).
Normoglycemia	No Diabetes, and not meeting the criteria for Prediabetes at baseline.

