16.1.5. Subgroup Analyses of Adverse Events

Subgroup analyses of patient incidence and EAIR of TEAE for age group (<65, 65-75, ≥ 75 years), sex, and race (white vs non-white), baseline eGFR category (<60, 60-90, ≥90 mL/min/1.73m²), baseline glycemic status (normoglycemic, prediabetes, and diabetes), baseline ezetimibe use (yes/no) will be presented by SOC and PT in descending order frequency.

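### SAP 16.1.4 divides AESI rates by whole-SAS exposure, in conflict with SAP 7.4.1 and 16.1.2, which confine new-onset diabetes and worsening hyperglycemia to baseline subsets

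*SAP*

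**What the plan says.** **The rate formula (SAP 16.1.4).** Its scope is general: "For all treatment-emergent AEs, SAEs, and AESIs, exposure-adjusted incidence rates (EAIR) will be calculated by preferred terms (PTs) and by treatment group". Each patient contributes time "from the date of the first dose of IMP to the date of the first event (PT), or the DLASMT" if there was no event. The rate is the number of patients with a first event "divided by the sum of duration of exposure over all patients in the SAS in the treatment group", per 100 patient-years. The section makes no exception for an AESI limited to a subset and does not refer to 7.4.1.

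**Who can have the two glycemic AESIs (SAP 16.1.2).** "The NODM AESI is applicable only for patients with baseline glycemic status" of No Diabetes. In turn, "Worsening Hyperglycemia AESI is applicable to patients with baseline glycemic status of Diabetes".

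**The analysis population (SAP 7.4.1).** For the safety analyses of these two AESIs, "the SAS is used with subpopulations defined according to the baseline glycemic status": No Diabetes for new-onset diabetes, Diabetes for worsening hyperglycemia. The section does not mention exposure, rates or denominators.

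**Subgroup rates (SAP 16.1.5).** TEAE incidence and EAIR are also planned, by SOC and PT, within "baseline glycemic status (normoglycemic, prediabetes, and diabetes" strata.

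**The concern.** An incidence rate should divide events by the time of those who could have had the event. Under 16.1.2, a patient with diabetes at baseline cannot be counted as an NODM event, and a patient without it cannot be counted as a worsening hyperglycemia event. The 16.1.4 denominator takes in both groups for both AESIs.

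Two programmers could therefore produce different rates from the same plan, one following 16.1.4 and the other 7.4.1. The literal version understates the absolute rate in each arm and shrinks any rate difference a reader takes between arms. If incidence percentages were restricted under 7.4.1 while rates followed 16.1.4, the tables would describe different populations without saying so. Diabetes and glycemia is a named AESI category in Protocol 15.8.1, so these rates are likely to be read closely.

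**Working it through.** The documents state no EAIR, no event rate for either AESI and no share of patients with diabetes at baseline. There is no planned figure to reproduce, so the check only sizes the effect of the literal formula.

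**Inputs from the documents**
- About 7000 patients per arm (SAP 8.1). This is the randomized number, used here for the SAS; it cancels out of the rates.
- Average follow-up of about 3.5 years (SAP 8.1), applied to every patient.
- Time stops at the first event (SAP 16.1.4).

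**Assumed inputs**
- Share d of patients with diabetes at baseline: 10% to 60%, with the same potential follow-up in both groups.
- At-risk event rate λ: 2, 5 or 10 per 100 PY, exponential time to first event.
- True rate ratio of 1.2, used only for the between-arm check.

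**Formulas.** With n eligible and m ineligible patients in an arm and T = 3.5:
- Events E = n(1 - exp(-λT))
- Eligible person-years P = E/λ
- Restricted rate = 100 × E/P = 100λ
- Literal rate = 100 × E/(P + mT)
- Dilution factor = P/(P + mT)

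The factor is the eligible share of the person-time counted. Because eligible time stops at the event, it falls slightly below (1-d) for NODM and d for worsening hyperglycemia when d is a share of patients.

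**One case in full: d = 30%, λ = 5 per 100 PY.** Here 1 - exp(-0.175) = 0.1605.
- NODM: n = 4900, E = 787, P = 15,733, mT = 2100 × 3.5 = 7350. Literal rate = 100 × 787/23,083 = 3.41; factor 0.68.
- Worsening hyperglycemia: n = 2100, E = 337, P = 6743, mT = 4900 × 3.5 = 17,150. Literal rate = 100 × 337/23,893 = 1.41; factor 0.28.

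**Across d, at an at-risk rate of 5 per 100 PY**

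| d | NODM, literal (factor) | Worsening hyperglycemia, literal (factor) |
|---|---|---|
| 10% | 4.46 (0.89) | 0.46 (0.09) |
| 30% | 3.41 (0.68) | 1.41 (0.28) |
| 50% | 2.39 (0.48) | 2.39 (0.48) |
| 60% | 1.90 (0.38) | 2.90 (0.58) |

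Over the whole grid the NODM factor runs from 0.36 (d = 60%, rate 10) to 0.90 (d = 10%, rate 2). The worsening hyperglycemia factor runs from 0.09 (d = 10%, rate 10) to 0.59 (d = 60%, rate 2).

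**A bound that does not need d.** Within an arm the two factors are at most the non-diabetic and diabetic shares of total follow-up time, so they sum to no more than 1. Under the literal formula, at least one of the two rates is therefore half its at-risk value or less.

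**Between-arm comparison, d = 30%, at-risk rates 5 and 6 (difference 1.00, ratio 1.20).** At rate 6, 1 - exp(-0.21) = 0.1894.
- NODM: E = 928, P = 15,469, literal rate = 100 × 928/22,819 = 4.07. Difference 4.07 - 3.41 = 0.66; ratio 1.19.
- Worsening hyperglycemia: E = 398, P = 6630, literal rate = 100 × 398/23,780 = 1.67. Difference 1.67 - 1.41 = 0.26; ratio 1.19.

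Over the whole grid an assumed ratio of 1.20 becomes 1.17 to 1.20.

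**The case against.** The strongest reply is that SAP 7.4.1 already settles the matter. It sets the population for safety analyses of these AESIs, an EAIR of an AESI is such an analysis, and a specific rule would ordinarily govern a generic formula. On that reading percentages and rates share the same subset and nothing is diluted. This stands in part: 7.4.1 does give the right population, and an analyst could follow it. But it says nothing about exposure. Section 16.1.4 is the only place where an EAIR denominator is defined; it includes AESIs explicitly and has no cross-reference. The opening of Section 16 also makes the SAS the set for all safety analyses. The plan does not say which section prevails.

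Second, 16.1.5 already plans rates within baseline glycemic strata. That supplies term-level rates in the diabetes stratum, which helps for worsening hyperglycemia because that AESI is defined by preferred terms. It does not supply the NODM AESI rate. That AESI also counts committee-verified cases, medication starts and laboratory criteria, and the strata split the No Diabetes group in two.

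Third, 16.1.4 works by preferred term, and for an ordinary TEAE term whole-SAS exposure is correct. That is true, and it leaves unclear whether an AESI-level NODM rate is intended at all. The AESI definitions in Appendix 7 are not in the text available for this review, so they could not be checked.

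A reader might go further and infer that every AESI rate is wrong, or that the trial will report rates far too low. The documents support neither. Only the two AESIs limited by baseline glycemic status are touched, the dilution arises only if 16.1.4 is programmed literally, and the shortfall for either one depends on a diabetes share that is not given.

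**Conclusion.** The point holds as an inconsistency between sections with a conditional consequence. SAP 16.1.4 states a denominator that does not match the populations fixed in 7.4.1 and 16.1.2 for two AESIs. Programmed as written, it gives absolute rates reduced to roughly (1-d) and d of the at-risk rates, with rate differences shrinking to a similar degree. The numerical ranges rest on the assumed d, assumed event rates, constant hazards and equal follow-up; only the bound that at least one rate is halved or worse is free of the assumed d.

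The consequence is confined to descriptive safety figures. Section 16 plans no between-group testing of safety data unless specified, the rate ratio is nearly unchanged, and no primary or key secondary result is involved. A reader might also infer that correcting the denominator would make the drug look worse. That is not established: the rates rise in both arms, any difference widens in whichever direction it lies, and Protocol 6.2 hypothesizes that the drug delays new-onset diabetes. The correction is worth making, but the trial's conclusions do not depend on it.

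**What to change.** Add to SAP 16.1.4: *For the NODM AESI, events and person-time are restricted to SAS patients with baseline status No Diabetes; for worsening hyperglycemia, to SAS patients with baseline status Diabetes (Section 7.4.1).*

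Because 16.1.4 is written by preferred term, it would help to state in the same place whether an AESI-level NODM rate is intended and, if so, which date counts as the first event when the case rests on a laboratory value, a medication start or committee verification.

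The cost is one sentence, or two with the clarification, and a population flag in the affected tables. No new data are needed. Compared with the literal formula, the absolute rates for these two AESIs become higher in both arms.
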